1. STUDY DETAILS

1.1 Study objectives

1.1.1 Primary objectives

Primary Objective:	Outcome Measure:
To demonstrate the short-term (up to 12 weeks) efficacy of AZD0585 2 g and 4 g compared to Placebo (corn oil) in Japanese patients with hyperlipidemia accompanied by hypertriglyceridemia (TG in the range 150-499 mg/dL)	Placebo-corrected percent change in serum TG level from baseline to Week 12 Endpoint.
To evaluate the long-term (up to 52 weeks) safety of AZD0585 administration in patients with hyperlipidemia accompanied by hypertriglyceridemia (TG in the range 150-499 mg/dL)	Adverse events, brief physical findings/clinical assessments, ECG assessments, vital signs and laboratory evaluations.

1.1.2 Secondary objectives

Secondary Objective:	Outcome Measure :
To assess the effect of each dose of AZD0585 on fasting serum lipid profile	Percent change in each serum lipid level from baseline to Week 12 Endpoint in serum lipid profile including total cholesterol (TC), LDL-C, VLDL-C, HDL-C and non-HDL-C.
To assess the effects of each dose of AZD0585 in parameters shown as outcome measure for the objective	Apolipoprotein (Apo) A-I, Apo A-II, Apo B, Apo B48, Apo C-II, Apo C-III, and Apo E based on percent changes from baseline to Week 12.
	• Plasma fatty acids profile: EPA, DHA, AA and EPA/AA ratio up to Week 12.
	Small dense LDL and LDL-C/Apo B ratio based on percent changes from baseline to Week 12.
	• Lp(a), RLP-C, PCSK9 and hs-CRP up to Week 12.

1.1.3 Exploratory objectives

Exploratory Objective:	Outcome Measure :
To assess the time-course of efficacy-related parameters profile up to Week 52 and explore the	• Fasting serum lipid profile including TG, TC, LDL-C, VLDL-C, HDL-C and non-HDL-C.
efficacy characteristics of long-term use of AZD0585 2 g/4 g vs. Placebo.	• Apo A-I, Apo A-II, Apo B, Apo B48, Apo C-II, Apo C-III, and Apo E.
	 Plasma fatty acids profile: EPA, DHA, AA, and EPA/AA ratio.
	• Small dense LDL and LDL-C/Apo B ratio.
	• Lp(a), RLP-C, PCSK9 and hs-CRP.

1.2 Study design

This is a randomised, double-blinded, placebo controlled, study employing 3 arm parallel groups to evaluate efficacy of 12 weeks and safety of 52 weeks of AZD0585 administration in patients with hyperlipidemia accompanied by hypertriglyceridemia (TG in the range 150-499 mg/dL).

Total 375 subjects will be randomised to 3 cohorts, A) Placebo, B) AZD0585 2 g, and C) AZD0585 4 g, at a ratio of 1:2:2, respectively. The efficacy will be evaluated as placebo-corrected percent change TG reduction at 12 weeks from the baseline TG level. The safety will be evaluated as adverse events and other safety parameters (vital sign, clinical laboratory test, etc) during 52-week treatment period.

[figure not shown]
- A. Placebo (corn oil) 4 g once daily (n=75)
- B. AZD0585 2 g (+placebo 2g) once daily (n=150)
- C. AZD0585 4 g once daily (n=150)

[figure not shown]
Randomisation will be stratified by the following factors to ensure equal representation across all treatment groups;

- Current use of statin (yes vs. no) at baseline
- Baseline TG level <300 or ≥300 mg/dL

In addition to the stratified randomisation the recruitment of patients will monitored so that approximately 50% of total randomised patients are statin users.

Figure 1 Study flow chart

E: Enrolment, R: Randomisation

- a An efficacy primary analysis will be done at Visit 8.
- b The data of interim analysis will be cut off when last subjects comes by Visit 11. An interim analysis will include all patients' data available until data cut-off, including primary/secondary analysis at Week 12 Endpoint for efficacy as well as safety evaluation based on 24-week or longer exposure to study drug.

1.3 Number of subjects

A common standard deviation of 24% is assumed for primary efficacy variable (Percent change from baseline to Week 12 Endpoint in serum TG). 150 patients in both of AZD0585 2 g and AZD0585 4 g and 75 patients in Placebo will ensure the power for detecting 12.5% difference of AZD0585 each dose vs. Placebo to be at least 92%, based on t-test with two-sided significance level of 0.05/2= 0.025, where approximate normality is assumed for the primary efficacy variable and significance level is conservatively adjusted for multiplicity for two comparisons by Hochberg procedure.

In the above calculation, it was assumed that a total of 375 patients are to be randomised to Placebo, AZD0585 2 g, AZD0585 4 g with ratio of 1:2:2 and that proportion of randomised patients not contributing primary analysis at Week 12 endpoint is negligible.

In addition, the above sample size is expected to be sufficient to provide long term safety data of more than 100 Japanese patients treated by AZD0585 2 g or by AZD0585 4 g for as long as

1 year assuming 10-15% drop out rate during 52-week treatment period, in accordance with Japan regulatory requirement.

2. ANALYSIS SETS

2.1 Definition of analysis sets

Randomised set: all patients who received randomisation number.

Full Analysis Set (FAS): all randomised set who had both any baseline and any post-baseline efficacy measurements. Patients will be analyzed according to their randomised treatment. FAS will be considered primary analysis set used for all efficacy evaluation.

Per Protocol Set (PPS): all patients in FAS who completed the first 12-week treatment period without any significant protocol deviations affecting primary efficacy evaluations. All criteria to exclude patients from the PPS will be made prior to the unblinding of the study. Patients will be analyzed according to their randomised treatment. Analyses on PPS will be of supportive purpose and limited to primary and important efficacy variables. Per Protocol Set will be subset of FAS, typically including patients without any important protocol deviations listed in Table 1.

Safety Analysis set (SAF): all patients who took at least on dose of double-blind study medication. Patients will be analyzed according to the actual study medication received. If a patient has received different study medications, the study physician and the clinical team will determine treatment group on a case-by-case basis, prior to unblinding.

2.2 Violations and deviations

Protocol deviations will be reviewed in a blinded fashion by the study team prior to database lock. The important protocol deviations which lead to exclusion from Per-protocol analysis are listed in the Table 1. All decisions to exclude subjects and/or data from the Full Analysis Set to form the Per-Protocol Analysis Set will be agreed by the study team and documented prior to the unblinding of the study.

Table 1 List of important protocol deviations

Protocol deviations

- 1 Discontinued study before attending 12-week visit
- 2 Subjects who took wrong study medication during initial 12-week treatment period
- 3 Subjects who were not compliance to study drug (< 80% or > 120%) during the initial 12-week treatment period
- 4 Subjects who changed the dose/regimen of statin during the initial 12-week treatment period

Protocol deviations

5 Subjects who newly introduced additional lipid lowering drugs/supplements during the initial 12-week treatment period

3. ANALYSIS VARIABLES

3.1 Primary Efficacy variable

Primary efficacy variable is percent change from baseline to the Week 12 Endpoint in serum triglyceride (TG).

3.2 Secondary efficacy variables

Secondary efficacy variables are listed below.

3.2.1 Fasting lipids

- Percent change from baseline to the Week 12 Endpoint in total cholesterol (TC)
- Percent change from baseline to the Week 12 Endpoint in high-density lipoprotein-cholesterol (HDL-C)
- Percent change from baseline to the Week 12 Endpoint in non- high-density lipoprotein-cholesterol (non-HDL-C)
- Percent change from baseline to the Week 12 Endpoint in very-low-density lipoprotein-cholesterol (VLDL-C)
- Percent change from baseline to the Week 12 Endpoint in low-density lipoproteincholesterol (LDL-C)

3.2.2 Secondary variables other than fasting lipids

- Percent change from baseline to Week 12 in Apo-lipoprotein A-I (Apo A-I)
- Percent change from baseline to Week 12 in Apo-lipoprotein A-II (Apo A-II)
- Percent change from baseline to Week 12 in Apo-lipoprotein B (Apo B)
- Percent change from baseline to Week 12 in Apo-lipoprotein B48 (Apo B48)
- Percent change from baseline to Week 12 in Apo-lipoprotein C-II (Apo C-II)
- Percent change from baseline to Week 12 in Apo-lipoprotein C-III(Apo C-III)
- Percent change from baseline to Week 12 in Apo-lipoprotein E (Apo E)
- Percent change from baseline to Week 12 in Eicosapentaenoic Acid (EPA)
- Percent change from baseline to Week 12 in Docosahexaenoic Acid (DHA)
- Percent change from baseline to Week 12 in Arachidonic acid (AA)
- Percent change from baseline to Week 12 in EPA/AA ratio

- Percent change from baseline to Week 12 in Small dense LDL
- Percent change from baseline to Week 12 in LDL-C/Apo B ratio
- Percent change from baseline to Week 12 in Lipoprotein(a) (Lp(a))
- Percent change from baseline to Week 12 in Remnant Lipoprotein Cholesterol (RLP-C)
- Percent change from baseline to Week 12 in Proprotein convertase subtilisin/kexin type 9 (PCSK9)
- Percent change from baseline to Week 12 in High-sensitivity C-reactive protein (hs-CRP)

3.3 Exploratory efficacy variables

Exploratory efficacy variables are time course from baseline to Week 52 of following variables.

- Fasting serum lipid profile including TG, TC, LDL-C, VLDL-C, HDL-C and non-HDL-C
- Apo A-I, Apo A-II, Apo B, Apo B48, Apo C-II, Apo C-III, and Apo E
- Plasma fatty acids profile: EPA, DHA, AA, and EPA/AA ratio
- Small dense LDL and LDL-C/Apo B ratio
- Lp(a), RLP-C, PCSK9 and hs-CRP

3.4 Primary Safety variables

Safety of AZD0585 2g/4g treatment will be analyzed when administered for up to 52 weeks. The safety evaluations will include analyses of:

- Adverse events
- (Safety) Laboratory parameters
- Electrodiagram (ECG)
- Vital signs
- Physical examination and findings

4. ANALYSIS METHODS

4.1 General principles

4.1.1 Objectives and hypotheses

4.1.1.1 Primary Efficacy Objective

The primary efficacy objective of this study is to demonstrate the efficacy of AZD0585 2 g and 4 g when compared with Placebo using the percent change from baseline in TG to Week 12 Endpoint as a primary efficacy variable.

The null hypothesis H_{01} , H_{02} given below will be tested against the alternative hypothesis H_{A1} , H_{A2} .

 H_{01} : μ_{E2} - μ_{P} = 0, H_{02} : μ_{E4} - μ_{P} = 0

 $H_{A1} \colon \quad \mu_{E2} \text{ - } \mu_{P} \neq 0, \qquad \quad H_{A2} \colon \quad \mu_{E4} \text{ - } \mu_{P} \neq 0$

where μ_{E2} , μ_{E4} , μ_{D} denote true means of AZD0585 2g, AZD0585 4g, Placebo respectively.

In order to protect family wise error rate (FWER) to be 5%, superiority of AZD0585 2 g vs. Placebo and superiority of AZD0585 4 g vs. Placebo will be tested based on Hochberg procedure using two-sided significance level of 0.05. If a p-value for each hypothesis is less than 0.05/2 = 0.025, the corresponding hypothesis claimed to be demonstrated. If both p-values (for 2g and 4g dose groups) are less than 0.05, then the both hypotheses are claimed to be demonstrated.

All analyses other than analysis of the primary efficacy endpoint will be interpreted descriptively. Consequently, no adjustments for multiplicity will be necessary for such analyses. Ninety-five percent confidence intervals will be calculated, where appropriate, as measures of study precision. P-values may be calculated but are to be regarded as descriptive.

4.1.1.2 Primary Safety Objective

The other primary objective is to evaluate the safety of long-term (up to 52 weeks) treatment by AZD0585 2g and AZD0585 4g. No formal statistical hypothesis test will be carried out for this safety primary objective.

4.1.2 Definitions

4.1.2.1 Baseline

For fasting lipids (TG, TC, HDL-C, non-HDL-C, VLDL-C, and LDL-C), baseline is defined as an average of week -4, week -2 (, week -1 if patients attended Visit 3a) and week 0 measurements.

For the other efficacy parameters listed in section 3.2.2 as well as safety parameters, baseline value is defined as the last non-missing assessment on or prior to the date of the first dose of the study medication. In typical case, week 0 is considered as baseline.

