4. STUDY PLAN AND TIMING OF PROCEDURES

Table 1 Study Plan

	Screening period				Treatment period													Withdrawal visit ^a				
	-8	-4	-2		0	4	8	10	12	16	20	24	28	32	36	40	44		48	52		
Week	1	2	3	3 ^a	4 ^c	5	6	7	8	9	10	11	12	13	14	15	16	17	18	19		
Visit window (days)	± 3	± 3	± 2		0	± 2	± 2	± 2	± 2	± 7	± 7	± 7	± 7	± 7	± 7	± 7	± 7	± 7	± 7	± 7		
Informed Consent	X																					
Eligibility Review	←				→																	
Randomisation					X																	
Demography	X																					
Medical History/Surgical History, Prior Medications	←				→																	
Brief Physical Findings ^d	X								X													X
Clinical Assessments ^e	X				X	X	X	X	X	X	X	X	X	X	X	X	X	X	X	X	X	X
Vital Sign	X				X	X	X		X	X	X	X	X	X	X	X	X	X	X	X	X	X
Fasting Lipid Panel (TG, TC, LDL-C, HDL-C, non-HDL-C, VLDL-C)	X	X	X	X	X	X	X	X	X	X	X	X	X	X	X	X	X	X	X	X	X	X
Fasting special lipid markers (RLP-C, Apo B and Apo B48)	X				X				X			X										X
Fatty acids profile (EPA, DHA, AA, and EPA/AA ratio)	X				X				X			X										X
Small dense LDL					X				X			X										X

Table 1 Study Plan

	Screening period				Treatment period														With- drawal visit ^a	
	-8	-4	-2		0	4	8	10	12	16	20	24	28	32	36	40	44	48		52
Week	1	2	3	3 ^a	4 ^c	5	6	7	8	9	10	11	12	13	14	15	16	17	18	19
Visit window (days)	± 3	± 3	± 2		0	± 2	± 2	± 2	± 2	± 7	± 7	± 7	± 7	± 7	± 7	± 7	± 7	± 7	± 7	
Apo except Apo B (A-I, A-II, C-II, C-III and E)					X				X			X			X				X	
hs-CRP					X				X			X			X				X	
Fasting special lipid markers (Lp(a), PCSK9)					X				X			X			X				X	
Clinical Chemistry	X	X			X	X			X	X		X			X				X	
Haematology	X	X			X	X			X	X		X			X				X	
Thromboplastin time (PT), Partial thromboplastin time (PTT)		X			X				X			X			X				X	
Urinalysis	X	X			X	X			X	X		X			X				X	
HbA1c	X				X				X			X			X				X	
Assessment of renal function (Estimated glomerular filtration rate [eGFR], Albumin Creatinine Ratio [ACR])	X																			
TSH	X																			
Urine Pregnancy Test	X				X														X	

Table 1 Study Plan

Week	Screening period				Treatment period														Withdrawal visit ^a			
	-8	-4	-2		0	4	8	10	12	16	20	24	28	32	36	40	44	48		52		
Visit	1	2	3	3a ^b	4 ^c	5	6	7	8	9	10	11	12	13	14	15	16	17	18	19		
Visit window (days)	± 3	± 3	± 2		0	± 2	± 2	± 2	± 2	± 7	± 7	± 7	± 7	± 7	± 7	± 7	± 7	± 7	± 7	± 7		
ECG	X				X				X			X			X					X		
Diet Counselling on Therapeutic Lifestyle Changes (TLC) diet	X	X	X		X	X	X	X	X	X	X	X	X	X	X	X	X	X	X			

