4.1.2.2 Endpoints

For fasting lipids (TG, TC, HDL-C, non-HDL-C, VLDL-C, and LDL-C), the Week 12 Endpoint is defined as an average of week 10 and week 12 measurements. For discontinued subjects, average of last non-missing two consecutive measurements up to week 12 is used as the week 12 Endpoint. If only a single measurement is available for a patient, it is used as the week 12 Endpoint.

For the other secondary efficacy parameters listed in section 3.2.2, if no measurement is available at Week 12, the last post-baseline single measurement up to Week 12 will be used if appropriate. Such cases will be presented as Week 12 (LOCF).

For any variables, last non-missing measurement up to Week 24/52 will be employed for Week 24/52(LOCF) evaluation if appropriate.

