4.2.2 Efficacy

4.2.2.1 Analysis of primary efficacy variable

The primary efficacy variable is the percent change in TG from baseline to week 12 Endpoint. The primary efficacy analysis for the percent change in TG will be based on analysis of covariance (ANCOVA) model, with fixed categorical effects of treatment, statin usage, as well as continuous fixed covariate of baseline TG value. For comparisons of each AZD0585

dose vs. Placebo pair-wise comparison, variance estimated from each pair will be employed. Primary analysis will be carried out for FAS.

The model will provide least-squares (LS) mean estimates, standard errors and 2-sided 95% confidence intervals (CIs) for mean change at Week 12 Endpoint within and between treatments. Unadjusted two sided P-values will be calculated based on the model. Confirmatory hypothesis testing will be based on Hochberg procedure as described in section 4.1.1.1. If a (two-sided) p-value for either dose is less than 0.05/2 = 0.025, superiority of the corresponding AZD0585 dose to Placebo will be claimed. If both p-values (for 2g and 4g dose groups) are less than 0.05, then superiority of both AZD0585 doses to placebo will be claimed.

Sensitivity analysis of primary efficacy variable

To assess the robustness of the primary efficacy analysis, and to compare the results with previous studies, the sensitivity analyses on the primary efficacy variable will be carried out using the following approaches.

Per Protocol analysis

Primary analysis by the same ANCOVA model for percent change in TG from baseline to week 12 Endpoint will be repeated for Per-Protocol Set.

Analysis based on log transformation

Change from baseline in log-transformed TG values at Week 12 Endpoint will be analyzed by ANCOVA model with fixed categorical effects of treatment, statin usage, as well as continuous fixed covariate of log-transformed baseline TG value. LSmeans and 95%CIs for each treatment and treatment difference will be back-transformed and presented as mean percent change from baseline and as relative treatment difference to Placebo in percent change. Nominal p-values will also be reported from the models. The detail of transforming quantity from analysis in log scale to percent change is provided in the table below:

Table 2 Transformation of quantities from log-transformed analysis

Quantities	Derivation
Adjusted mean percent change from baseline	$100 \times [exp(Adjusted mean change from baseline in natural logarithm) - 1]$

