4.2.2.2 Analysis of secondary efficacy variables

Fasting lipids (as defined in section 3.2.1)

The percent change from baseline of each fasting lipid parameter to the Week 12 Endpoint will be analyzed by ANCOVA model, with fixed categorical effects of treatment, statin usage, baseline TG strata (<300, >= 300 mg/dL) as well as continuous fixed covariate of corresponding baseline value. All the analyses will be carried out primarily for FAS and will be repeated for PPS.

The model will provide least-squares (LS) mean estimates, standard errors and 2-sided 95% confidence intervals for mean change at Week 12 Endpoint within and between treatments. Nominal two-sided p-values will also be displayed.

Other secondary efficacy parameters except for fasting lipids (as defined in section 3.2.2)

The percent change from baseline of each secondary efficacy parameter to Week 12 (LOCF) will be analyzed by ANCOVA model, with fixed categorical effects of treatment, statin usage, TG strata (<300, >= 300 mg/dL) as well as continuous fixed covariate of corresponding baseline value. All the analyses will be carried out for FAS only.

The model will provide least-squares (LS) mean estimates, standard errors and 2-sided 95% confidence intervals for mean percent change at Week 12 (LOCF) within and between treatments. Nominal two-sided p-values will also be displayed.

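### Eight secondary markers have a scheduled Week -8 sample that their ANCOVA does not use; as a second covariate it could cut variance by 0 to about 20%

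*SAP*

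**What the plan says.** **Sampling.** In Protocol section 4, Table 1, the rows "Fasting special lipid markers (RLP-C, Apo B and Apo B48" and "Fatty acids profile (EPA, DHA, AA, and EPA/AA ratio" are marked at Visit 1 (Week -8) and again at Visit 4 (Week 0). The row "Fasting Lipid Panel (TG, TC, LDL-C, HDL-C, non-HDL-C, VLDL-C" is marked at every visit, so LDL-C/Apo B can also be derived at Visit 1. That makes eight secondary markers with two scheduled pre-dose values. Small dense LDL, the other apolipoproteins, hs-CRP, Lp(a) and PCSK9 start only at Visit 4.

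**Baseline.** For fasting lipids, SAP 4.1.2.1 says "baseline is defined as an average of week -4, week -2 (, week -1 if patients attended Visit 3a) and week 0 measurements". Markers outside the panel follow a different rule: their "baseline value is defined as the last non-missing assessment on or prior to the date of the first dose of the study medication". Visit 1 therefore becomes a marker's baseline only when Visit 4 is missing.

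**Models.** The marker ANCOVA in SAP 4.2.2.2 has treatment, statin use, TG stratum and a "continuous fixed covariate of corresponding baseline value". The primary model in SAP 4.2.2.1 has treatment, statin use and a "continuous fixed covariate of baseline TG value". Neither has a Week -8 term. Protocol 8.5.1 and 8.5.2.1 specify the same covariates.

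**The concern.** The plan takes visit-to-visit noise in the lipids seriously. It averages three or four pre-dose values, and on the other side "the Week 12 Endpoint is defined as an average of week 10 and week 12 measurements". The eight markers get a single pre-dose value, which serves both as the denominator of the percent change (SAP 4.1.2.3) and as the only marker-specific covariate. Its noise goes straight into the residual.

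A second pre-randomisation value is already scheduled for each of them. Because it precedes randomisation, adjusting for it cannot bias the dose-placebo contrast. What is at stake is precision: the width of confidence intervals that SAP 4.1.1.1 itself offers as the measure of how precise the study is. No confirmatory claim depends on it.

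**Working it through.** **Inputs from the documents.** Visit times and samples: Protocol Table 1. Baseline, endpoint and model terms: SAP 4.1.2.1, 4.1.2.2, 4.2.2.1 and 4.2.2.2. Group sizes 75, 150 and 150, SD 24, difference 12.5, two-sided alpha 0.025: SAP 1.3.

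**Assumed.** The correlation of a marker between visits. The documents give none, so a range is shown.

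**1. The plan's own figure.** SE = 24 × √(1/75 + 1/150) = 3.394, and 12.5/3.394 = 3.683. Subtracting 2.241 gives 1.44, so power is 92.5% by the normal approximation, or 92.2% by the noncentral t with 223 df. This agrees with the stated minimum of 92% for TG. No precision target is given for the markers.

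**2. General formula for a marker.** Let a = corr(Week 0, Week 12), b = corr(Week -8, Week 0) and c = corr(Week -8, Week 12). Adding Week -8 to a model that already has Week 0 reduces residual variance by

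(c − ab)² / [(1 − a²)(1 − b²)].

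**3. Equal correlation (a = b = c = r).** This becomes r²/(1 + r)². Confidence intervals narrow by 1 − √(1 − reduction).

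| r | Variance reduction | CI narrower by |
|---|---|---|
| 0.3 | 0.09/1.69 = 5.3% | 2.7% |
| 0.5 | 0.25/2.25 = 11.1% | 5.7% |
| 0.7 | 0.49/2.89 = 17.0% | 8.9% |
| 0.8 | 0.64/3.24 = 19.8% | 10.4% |

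At r = 0.9 the reduction would be 22.4%.

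**4. Correlation that decays with time.** Week -8 lies 20 weeks from Week 12; Week 0 lies 12 weeks from it.
- Pure first-order autoregression: c = ab, so the reduction is 0.
- Stable patient level plus decay plus measurement error: 2.0 to 9.4% over the mixes tried. At the top end, 50% of variance is stable, 20% halves its correlation every 4 weeks and 30% is error. Then a = 0.525, b = 0.55, c = 0.5063, and (0.5063 − 0.2888)²/(0.7244 × 0.6975) = 9.4%.

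**5. Visit 1 only weakly related to later visits**, as after a washout. With a = 0.7 and b = c = 0.4: (0.40 − 0.28)²/(0.51 × 0.84) = 3.4%. With b = c = 0.2: 0.7%.

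**6. On the SAP's percent-change scale.** A simulation (log-normal values, log SD 0.35, equal correlation, Week 0 as denominator, Visit 1 as covariate) gave 8.3% at r = 0.5, 13.5% at 0.7 and 16.4% at 0.8. These are somewhat below the closed form.

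**7. Covariate or average?** In the same simulation, averaging Visit 1 into the baseline gave 21 to 23%, but it changes the variable being analysed and relies on Visit 1 being as good as Week 0. In the weak case of step 5, calculated by ANCOVA on the unscaled values, averaging *raises* variance by 11 to 30%. A covariate lets the data set the weight.

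**8. Cost of the term.** A pairwise comparison of 225 patients with five parameters leaves 220 residual df. One more term costs about 1/220 = 0.5% of variance.

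**9. TG for comparison.** TG would go from three to four pre-dose values, with two post-dose values averaged. Under equal r, residual variance with k pre-dose values is (1 + r)/2 − k r²/[1 + (k − 1)r]. At r = 0.5 this is 0.375 for k = 3 and 0.350 for k = 4, a 6.7% reduction; at 0.7 it is 8.3% and at 0.8 it is 9.0%. With decay it is 0.5 to 4.6%; in the weak case of step 5, 0.3 to 1.3%. Over r = 0.3 to 0.9 and the decaying cases, the 92.2% power would become about 92.4 to 94.6%.

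**The case against.** **The plan contains no error.** An ANCOVA on one baseline value is conventional, valid and pre-specified, and protocol and SAP agree on it. The comparisons are descriptive with no power target, and even the larger gains narrow an interval by only about a tenth. This stands; it limits the point to an efficiency recommendation.

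**Visit 1 may describe a different state.** Protocol 3.2 bars omega-3 products within 8 weeks before randomisation, Protocol 4.1 bars non-statin lipid drugs during the 8-week screening, and Table 1 starts diet counselling at Visit 1. For some patients the Visit 1 value, above all EPA, DHA and EPA/AA, may precede those changes. This also stands. It is a reason to keep Visit 1 out of the baseline average and to expect little gain for the affected markers. It does not make a covariate invalid.

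**Stronger readings that the documents do not support:**
- *That every patient has the value and no baseline uses it.* Table 1 shows scheduling only, and the last-non-missing rule uses Visit 1 when Visit 4 is missing.
- *That a fixed share of variance is lost.* Any single figure assumes a correlation that is nowhere stated; the gain can be nil.
- *That the primary TG model should change.* TG already has at least three pre-dose values in its baseline and its stated power. Its covariates are fixed in the protocol synopsis and 8.5.1, and reopening a confirmatory model for at most about two power points is hard to justify. The five other panel lipids also have the multi-visit baseline, so the case is weaker for them too.

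**Conclusion.** The point holds as a modest, low-cost improvement for RLP-C, Apo B, Apo B48, EPA, DHA, AA, EPA/AA and LDL-C/Apo B. Using the scheduled Visit 1 value as a second covariate could reduce the variance of the dose-placebo comparisons by 0 to about 20%. The upper part of that range needs Week -8 to predict Week 12 as well as Week 0 does, with r near 0.8. With decaying correlation or a pre-washout Visit 1, about 0 to 9% is the fair expectation. For TG the gain would be 0 to about 9%, which does not warrant touching the confirmatory analysis. The conclusion that adjustment is unbiased rests only on Visit 1 preceding randomisation; the size rests entirely on the assumed correlations.

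**What to change.** Before the sponsor is unblinded for the interim analysis (SAP section 5):

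1. In SAP 4.2.2.2, add the Visit 1 (Week -8) value as a second continuous covariate for the eight markers.
2. Keep Week 0 as the percent-change baseline; do not average Visit 1 into it.
3. Replace a missing Visit 1 value by the overall mean, ignoring arm. State also what is done when Visit 1 is already serving as baseline because Visit 4 is missing.
4. Record the departure from Protocol 8.5.2.1 in SAP section 6.
5. Leave the primary TG ANCOVA unchanged. If Visit 1 TG is of interest, pre-specify it in a supportive ANCOVA only.

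The cost is SAP wording, one model term and one degree of freedom, with no new samples. The downside is little or no gain for markers disturbed by washout or diet counselling. Made after unblinding, the same choice could look data-driven and should then be labelled post hoc.
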